**LIST OF ABBREVIATIONS**

AE	Adverse Event
ANCOVA	Analysis of Covariance
b.i.d	bis in die
BMI	Body Mass Index
CI	Confidence Interval
CRP	C-reactive Protein
CV	Coefficient of Variation
ECG	Electrocardiogram
eCRF	Electronic Case Report Form
FAS	Full Analysis Set
IMP	Investigational Medicinal Product
KM	Kaplan Meier
LS Means	Least Square Means
MedDRA	Medical Dictionary for Regulatory Activities
PDC	Protocol Deviation Criteria
PPAS	Per-Protocol Analysis Set
PT	Preferred Term
RAS	Randomised Analysis Set
SAP	Statistical Analysis Plan
SAS	Safety Analysis Set
SD	Standard Deviation
SE	Standard Errors
SOC	System Organ Class
SoC	Standard of Care
TEAE	Treatment-Emergent Adverse Event
WHO Drug	World Health Organization Drug Dictionary

## 1 INTRODUCTION

This document details the statistical analysis of the data that will be performed for the Vicore Pharma AB study: A randomised, double-blind, placebo-controlled, Phase 2 trial investigating the safety and efficacy of C21 in hospitalised subjects with COVID-19 infection not requiring mechanical ventilation.

The proposed analysis is based on the contents of the Final Version 1.0 of the protocol (dated 24 April 2020) and Final Version 2.0 of the protocol (dated 14 August 2020). In the event of future amendments to the protocol, this statistical analysis plan (SAP) may be modified to account for changes relevant to the statistical analysis.

The table, listing and figure shells are supplied in a separate document.

## 2 STUDY OBJECTIVES AND DESIGN

### 2.1 Study Objectives

#### 2.1.1 Primary Objective

The primary objective of the study is to investigate the efficacy of C21 200 mg daily dose (100 mg *b.i.d.*) on COVID-19 infection not requiring mechanical invasive or non-invasive ventilation.

#### 2.1.2 Secondary Objectives

The secondary objectives of the study are to evaluate the following of C21 200 mg daily dose (100 mg *b.i.d.*):

- Effect on inflammation,
- Safety profile.

#### 2.1.3 Exploratory Objective

To investigate a range of laboratory parameters as potential biomarkers of inflammation and viral load, following oral administration of C21 200 mg daily dose (100 mg *b.i.d.*).

### 2.2 Study Endpoints

#### 2.2.1 Primary Endpoint

The primary endpoint of the study is the change from baseline in C-reactive protein (CRP) after treatment with C21 200 mg daily dose (100 mg *b.i.d.*).

#### 2.2.2 Secondary Endpoints

The secondary endpoints are:

- Change from baseline in:
  - Body temperature,
  - IL-6,
  - IL-10,
  - TNF,
  - CA125,

- Ferritin.
- Number of subjects not in need of oxygen supply.
- Number of subjects not in need of mechanical invasive or non-invasive ventilation.
- Time to need of mechanical invasive or non-invasive ventilation.
- Time on oxygen supply\*.
- Adverse events (AEs).

\* This endpoint has been amended to remove reference to those not needing mechanical invasive or non-invasive ventilation. Further information can be found in Section 6.12 of this SAP.

### 2.2.3 Exploratory Endpoints

Blood samples will be stored for potential future analyses of biomarkers reflecting inflammation and lung injury.

## 2.3 Study Design

The trial will be conducted at trial sites within the UK (1 site) and India (up to 12 sites). Approximately 150 subjects will be enrolled and randomised to receive twice daily oral administration of either standard of care (SoC) + placebo (N=75) or SoC + C21 (N=75). Subjects will be treated for 7 days. All subjects will be followed up 7-10 days after receiving the last investigational medicinal product (IMP) dose (visit, or phone call if recovering at home).

## 2.4 Visit Structure

A total of 9 visits are defined:

- Visit 1: Screening,
- Visits 2–8: Treatment period,
- Visit 9: End-of-trial.

The maximum duration of the trial for any subject will be approximately 3 weeks, including a screening period of up to 3 days, a treatment period of 7 days and a visit for safety follow-up (end of-trial) to be conducted 7-10 days after the last dose of IMP.

The visit structure and scheduled assessments are detailed in Section 6, Tables 1 and 2 and Figure 1 of the protocol.

## 3 SAMPLE SIZE

Sample size is based on the assumption of a standard deviation (SD) of 60 mg/L for the change in CRP from baseline to average of last two assessments during one week of treatment. With 75 patients per group and a two-sided t-test at 10% significance level, there will be an approximative 80% power to detect a true reduction of 25 mg/L in C21 treated patients compared to placebo.

## 4 RANDOMISATION

Subjects will be randomised in a 1:1 schedule to receive either SoC + placebo or SoC + C21. Each subject will be assigned a randomisation (kit) number according to the randomisation schedule. Details of the randomisation including date of randomisation, assigned kit number, allocated treatment and treatment actually received will be listed.

### 4.1 Planned Treatment and Actual Treatment Received

Planned treatment is defined as the treatment to which the subject was randomised and will be determined by the original randomisation list. Actual treatment received is defined as the actual study treatment received regardless of randomised treatment.

Planned study treatment will be determined from the randomisation list supplied by Vicore Pharma AB as compiled by Ardena. Actual treatment received will be derived by reconciling the kit list number entered into the IMP Administration Electronic Case Report Form (eCRF) pages with the kit list also supplied by Vicore Pharma AB as compiled by Ardena. The kit list number will be entered into the eCRF at each dose of treatment. Subjects who were mis-randomised or received treatment incorrectly will be confirmed once the blind has been broken.

## 5 INTERIM ANALYSIS

No interim analysis will be performed.

## 6 ANALYSIS PLAN

### 6.1 General

Summary statistics for continuous variables will consist of number of non-missing observations (n), mean, SD, minimum, median and maximum, unless specified otherwise.

For categorical variables the number and percentage of subjects in each category will be presented, based on the number of non-missing observations apart from disposition of subjects, protocol deviations, background and demographic characteristics, prior and concomitant medications/procedures and AEs where the percentage will be based on the number of subjects in the analysis set with a missing category presented where applicable.

The mean and median will be displayed to 1 more decimal place than the original data values and the SD will be displayed to 2 more decimal places than the original data values. The minimum and maximum will be displayed to the same number of decimal places as the original data. Percentages will be displayed to 1 decimal place; except percentages will not be presented when the count is zero and 100% for count data will be presented as an integer.

All statistical tests will be performed using a two-tailed 10% overall significance level, unless otherwise stated. The null hypothesis at all times will be that the treatments are equivalent. All comparisons between the treatments will be reported with 90% confidence intervals (CIs) for the difference.

## 6.2 General Derivations

This section provides details of general derivations. Derivations specific to the parameter of interest are detailed within the specific SAP section.

### 6.2.1 Definition of Baseline

The derivation of baseline for CRP is described in Section 6.10.1 of this SAP.

Baseline for all other variables is defined as the last non-missing value (including scheduled and unscheduled assessments) prior to the subject receiving study treatment. For assessments performed at Visit 2 where it is not clear that the assessment was performed after study treatment administration, the assessment will be taken as a post-baseline assessment.

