### **6.10.1 Primary Endpoint**

The primary endpoint is the change in CRP from baseline to the mean of the last two non-missing scheduled assessments occurring during the seven day treatment period (Visits 2 to 8 and/or withdrawal). For subjects who do not complete treatment, the assessments up to and including the next-non missing assessment following the final administration of study treatment will be considered for inclusion in the mean.

The baseline CRP assessment is defined as the Visit 2 value supplied by the central laboratory where this assessment occurs prior to the first administration of study treatment. Should the Visit 2 assessment be taken after first administration of study treatment or be missing, the Visit 1 value will not be used and the baseline CRP assessment will remain missing. This avoids potential differences amongst local

laboratories that supply the Visit 1 CRP data following the protocol amendment of 14 August 2020. If necessary, the incorporation of Visit 1 local laboratory CRP values may be investigated post-hoc to support any conclusions of the CSR.

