### Imputation

Subjects with a missing baseline assessment or no post-baseline assessment of CRP will not be imputed and will not be included in the analysis.

Post-baseline assessments up to and including the next non-missing assessment (including those at or after the withdrawal assessment) following the final treatment administration will be considered as the treatment period for inclusion in the mean. The mean of their last two non-missing scheduled assessments during the treatment period, or a single CRP value where the subject has only completed one post-baseline CRP assessment, will be carried forward to represent state at the end of trial.

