### **6.10.2.1 Change from Baseline in Body Temperature and Laboratory Values**

#### Analysis

The change from baseline in body temperature, cytokines (IL-6, IL-10 and TNF), CA125 and ferritin will be analysed using the model outlined for the primary endpoint in Section 6.10.1 of this SAP.

In each case, the change in each parameter from baseline to the mean of the last two non-missing scheduled assessments during the treatment period will be analysed using an ANCOVA. For subjects who do not complete treatment, the assessments up to and including the assessment on the day of last study treatment administration will be considered for inclusion in the mean. The model will be fitted with the change from baseline as the dependent variable and study treatment as a fixed effect. The baseline value will be included as a covariate. Model assumptions will be checked and data transformations will be applied as described in Section 6.10.1.

These analyses will be reported as described for the primary endpoint in Section 6.10.1.

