#### Imputation

Data will be imputed for each parameter as detailed in Section 6.10.1 for the primary endpoint. For subjects who have no post-baseline assessments, no imputation will be applied and they will be excluded from the analysis.

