6.5.2 Treatment Period (Visits 2-8)

The treatment period lasts for 7 days (Visit 2-8). The procedures to be performed at each visit are specified below.

Vicore Pharma AB Version: 2.0 Trial ID: VP-C21-006 Date: 14-Aug-2020

Visit 2

Visit 2 can be scheduled as soon as the relevant screening assessments are available. Visit 2 must occur within 3 days from Visit 1 (screening).

The following procedures are performed:

- Re-evaluation of in- & exclusion criteria
- Short physical examination (including vital signs)
- Evaluation of ECG and laboratory results from Visit 1
- Assignment of randomisation number
- Concomitant medication
- Recording need of supplementary O₂
- Blood sampling for:
 - o CRP
 - Safety (haematology and biochemistry) (see Section 8.2.7)
 - o IL-6, IL-10, TNF, CA125, ferritin
 - o Biomarkers
- Urinalysis (dipstick for bilirubin, glucose, ketones, protein, specific gravity, urobilinogen and pH)
- IMP administration twice daily including diatery restrictions (see Section 5.3.2)
- Check of withdrawal criteria
- Adverse events

Visits 3-8

- Concomitant medication
- Short physical examination (including vital signs at the judgement of the Investigator)
- Recording need of supplementary O₂
- Blood sampling for
 - o CRP
 - o Safety (haematology and biochemistry) (see Section 8.2.7)
 - o IL-6, IL-10, TNF, CA125, ferritin
- Urinalysis (dipstick for bilirubin, glucose, ketones, protein, specific gravity, urobilinogen and pH)
- IMP administration twice daily including dietary restrictions (see Section 5.3.2)
- Check of withdrawal criteria
- Adverse events

In addition for Visit 8 (end-of-treatment) only:

- Pregnancy testing (urine dip-stick), if positive a blood pregnancy test must be performed to confirm positive pregnancy
- Biomarkers
- Drug accountability

Vicore Pharma AB Version: 2.0 Trial ID: VP-C21-006 Date: 14-Aug-2020

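### The Visit 2 timing rule in SAP 6.2.1 has its condition reversed: it contradicts the baseline definition and can cost some subjects their IL-6, IL-10, TNF, CA125 and ferritin baseline

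*SAP*

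**What the plan says.** SAP 6.2.1 first separates CRP from everything else: "The derivation of baseline for CRP is described in Section 6.10.1 of this SAP". In SAP 6.10.1 the CRP baseline is "defined as the Visit 2 value supplied by the central laboratory where this assessment occurs prior to the first administration of study treatment"; if that sample is late or absent, the CRP baseline stays missing.

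For the rest, SAP 6.2.1 gives two sentences. Sentence 1: "Baseline for all other variables is defined as the last non-missing value (including scheduled and unscheduled assessments) prior to the subject receiving study treatment". Sentence 2, on Visit 2 assessments: "where it is not clear that the assessment was performed after study treatment administration, the assessment will be taken as a post-baseline assessment".

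The secondary markers are analysed by ANCOVA on change from baseline (SAP 6.10.2.1), and "The baseline value will be included as a covariate". On missing data that section says "Data will be imputed for each parameter as detailed in Section 6.10.1 for the primary endpoint", and the rule it points to is "Subjects with a missing baseline assessment or no post-baseline assessment of CRP will not be imputed and will not be included in the analysis".

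The protocol describes marker sampling in more than one place. Section 6.5.2 lists "IL-6, IL-10, TNF, CA125, ferritin" at Visit 2, which is also the visit of the first dose. Table 2 starts these markers at Visit 2, and the Visit 1 blood-sampling list in section 6.5.1 omits them. Section 8.1.2 says they are drawn at every visit from screening onward.

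**The concern.** A rule that sends doubtful values to post-baseline should be triggered by doubt that the sample came before dosing. Sentence 2 is triggered by doubt that it came after. A sample with a documented pre-dose time meets that trigger, so sentences 1 and 2 classify it differently. A sample clearly taken after dosing, which ought to be post-baseline, falls outside sentence 2.

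The sentence is an operative derivation rule for every variable except CRP, and the programmer cannot repair it without making a choice. Changing 'after' to 'before' and changing 'post-baseline' to 'baseline' each restore sense, but they classify an untimed sample in opposite ways. For the five laboratory markers, that choice may decide whether a subject is analysed at all. These markers serve the secondary objective on inflammation.

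**Working it through.** **1. The plan's own figure.** The only power statement (SAP 3, protocol 13.1) concerns CRP: 75 per group, difference 25 mg/L, SD 60 mg/L, two-sided 10%. The noncentrality is (25/60) × √(75/2) = 2.55, and power = Φ(2.55 − 1.645) = 0.818 (0.815 with the exact noncentral t). The stated value of about 80% is reproduced. It does not bear on the wording, and no power is stated for the endpoints at issue.

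**2. The rule, case by case.**

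| Visit 2 value | Sentence 1 | Sentence 2 as written | 'after' changed to 'before' | 'post-baseline' changed to 'baseline' |
|---|---|---|---|---|
| Clearly pre-dose | Baseline | Post-baseline: conflict | Not caught; baseline by sentence 1 | Baseline |
| Untimed | Undecided | Post-baseline | Post-baseline | Baseline |
| Clearly post-dose | Not baseline | Not covered | Post-baseline | Not covered; not baseline by sentence 1 |

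The first and third rows show the reversal. The middle row shows that untimed samples go to post-baseline both in the current text and under the 'before' repair.

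**3. Is there an earlier value to fall back on?**

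- IL-6, IL-10, TNF, CA125, ferritin: no scheduled Visit 1 sample in protocol Table 2 or section 6.5.1, but one is implied by section 8.1.2. The documents conflict.
- Body temperature, vital signs, haematology, biochemistry and urinalysis: measured at Visit 1 (Tables 1 and 2). Baseline would move to a value 1 to 3 days older, given the visit window.
- CRP: governed by SAP 6.10.1, not by this rule.

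**4. From reclassification to exclusion.** If Table 2 and section 6.5.1 are right, a reclassified Visit 2 marker value leaves no scheduled pre-dose value. Neither the change score nor the covariate can then be formed, and the missing-data rule carried over from SAP 6.10.1 excludes the subject from that marker's ANCOVA.

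**5. Size.** The documents do not say how many Visit 2 samples lack a clear time. Let L be the share of subjects lost, assumed equal in the two arms. The standard error of the treatment difference is proportional to 1/√n, so it grows by 1/√(1 − L).

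| L (assumed) | n per arm, 75 × (1 − L) | 1/√(1 − L) | Rise in standard error |
|---|---|---|---|
| 5% | 71.25 | 1.026 | 2.6% |
| 10% | 67.5 | 1.054 | 5.4% |
| 20% | 60 | 1.118 | 11.8% |

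As an illustration only, borrowing the CRP standardised effect of 25/60, power would go from 0.818 to 0.800, 0.781 and 0.738.

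**6. Can a reclassified value count as an on-treatment value?** The endpoint is the mean of the last two scheduled assessments in the treatment period. A Visit 2 value enters only when the subject has at most one later assessment. A marker subject without a baseline is excluded anyway, so this mainly concerns temperature in subjects who stop very early.

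**The case against.** The strongest reply is that this is a slip whose meaning is plain. Sentence 1 governs any sample with a documented pre-dose time, and sentence 2 addresses only uncertain timing. The SAP consistently assigns uncertain timing to the treated period: unclear medications are concomitant (6.8), unclear adverse events are treatment-emergent (6.11.1), and incomplete dates take the worst case (6.2.3). For CRP it accepts a missing baseline rather than use a sample that is not pre-dose. On that view the intended word is 'before', and any loss of untimed samples follows from a deliberate conservative default. Blood-sampling and dosing times are required source data (protocol 11.2), so few samples should be untimed. Secondary endpoints are descriptive (SAP 6.10.4). Protocol 8.1.2 may supply a Visit 1 value. The order of the Visit 2 bullets in protocol 6.5.2 is not an instruction to sample before dosing.

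Most of this stands, and it limits the size of the problem. It does not remove the defect. The sentence is wrong as written, and SAP 6.12 does not correct it. Inferring the intended word from conventions elsewhere leaves the analysed population to a programmer's judgement. The 'before' reading also keeps the exclusion of untimed samples without saying what that means for markers that may have no other baseline.

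A reader might infer that sentence 2 removes the baseline of every subject for the five markers, leaving those ANCOVAs with no data. The documents do not support that. It would require sentence 2 to override sentence 1 for samples with a recorded pre-dose time, and nothing says that it does. The two sentences conflict; total loss is not a predicted outcome.

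**Conclusion.** The point holds as a wording defect with a limited, conditional consequence. It is certain from the text that the condition in sentence 2 is reversed, contradicts sentence 1 for clearly pre-dose values, and misses clearly post-dose ones. The primary CRP analysis is not affected.

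The loss of subjects from the IL-6, IL-10, TNF, CA125 and ferritin ANCOVAs rests on two conditions: that no Visit 1 sample exists, on which the protocol contradicts itself, and that some Visit 2 samples are untimed or otherwise reclassified. The 2.6% to 11.8% rise in standard error rests on an assumed loss of 5% to 20%, for which the documents give no basis; the true share may be smaller. That loss should not be blamed on the reversed word alone, since the likely one-word repair produces it too. The correction should be made, but this is not a threat to the trial's main conclusion.

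**What to change.** Before database lock and unblinding:

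1. Replace sentence 2 of SAP 6.2.1 so that a Visit 2 value timed before the first dose is baseline and one timed after it is post-baseline.
2. State one explicit default for Visit 2 values whose time is missing or unclear. For markers with no Visit 1 sample, take them as baseline. This is a defensible choice, but the protocol does not dictate it and it departs from the SAP's habit for unclear timing. Add a sensitivity analysis with the other classification.
3. List every Visit 2 value to which the default was applied.
4. Reconcile protocol 8.1.2 with Table 2 and section 6.5.1 on whether these five markers are sampled at Visit 1.

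The cost is a short SAP edit, one listing, one repeated set of secondary ANCOVAs and a protocol clarification. The downside of the default is that a few samples taken shortly after dosing may serve as baseline. This could happen in both arms, and the classification is made blind.

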### 6.2.2 Visit and Study Day

Throughout this SAP any references to "Visit XX" refer to the pre-specified visits defined in the protocol (where the study treatment administration visit is Visit 2).

Data listings by visit will additionally present study day, indicating the duration of time since first study treatment. Study day will be calculated relative to the first date of administration of study treatment (Study Day 1).

### 6.2.3 Incomplete Dates

For calculation purposes, incomplete dates will be completed using worst case. Further details are given in the relevant sections as required.

### 6.2.4 Non-numeric Values

For clinical laboratory parameters and cytokine data, in the case where a variable is recorded as ">x", "≥x", "<x" or "≤x" rather than an exact number, then for analysis purposes a value of x will be taken. Where a range of values is quoted the midpoint of the range will be taken. Where this process is not appropriate, further information will be detailed in the relevant section. The recorded value will be reported in listings.

### 6.2.5 Methods for Handling Withdrawals and Missing Data

Where imputation may be deemed appropriate, information is detailed in the analysis descriptions.

## 6.3 Analysis Sets

The **Enrolled Set** includes all subjects who provide informed consent irrespective of whether they received the study treatment.

The **Randomised Analysis Set (RAS)** includes all subjects who have been randomised, irrespective of whether they received the study treatment.

The **Full Analysis Set (FAS)** will consist of all subjects who have been randomised and received at least one dose of IMP and who have at least one post-baseline assessment of efficacy. A post-baseline assessment of efficacy includes an assessment of any of the parameters detailed in Section 6.10 of this SAP. Subjects will be analysed according to the treatment they are assigned to at randomisation, irrespective of what treatment they actually received.

The **Per-Protocol Analysis Set (PPAS)** will be a subset of the FAS and consist of all subjects without any major protocol deviations that are judged to compromise the analysis of the data. All protocol deviations will be judged as major or minor prior to database lock.

The **Safety Analysis Set (SAS)** consists of all subjects who have received at least one dose of IMP. Subjects will be analysed according to the treatment actually taken.

The list of subjects included in the PPAS will be agreed prior to breaking the blind once all study data is available. The definitions for the enrolled set, RAS, FAS and SAS are sufficient to determine the subjects included within these analysis sets and so do not require listing and agreeing prior to breaking the blind.

